6.4.3. Montreal Cognitive Assessment

The MoCA is a global cognitive screening test with favorable psychometric properties that has been shown to be more sensitive to executive impairment than the Mini-Mental State Examination. It screens 8 domains including: visuospatial/executive, naming, memory, attention, language, abstraction, delayed recall, and orientation. Assessments will be performed as specified in the Schedule of Study Procedures (). An example of the instrument is provided in [Appendix 2](#).

6.4.4. Valsalva Maneuver

The Valsalva maneuver is a breathing technique that can be used to help diagnose a problem with the autonomic nervous system (ANS). Changes in intrathoracic pressure produce autonomically modulated transient changes in HR and BP. The Valsalva maneuver will be performed as specified in the Schedule of Study Procedures ([Table 1](#)) only for subjects with PAF to confirm diagnosis.

6.4.5. OHQ Subject Training

Empirical evidence exists that the OHQ can accurately evaluate the severity of symptoms and the functional impact of symptomatic nOH as well as assess the efficacy of treatment⁹. To ensure that subjects are able to complete the OHQ questionnaires successfully with a complete understanding of the individual point differences on the scale as associated with their symptoms and to standardize the manner of completion of the 11-point scale from 0 to 10, the subjects will undergo OHQ training. Subjects should be rested prior to beginning the training. Assessments will be performed as specified in the Schedule of Study Procedures ([Table 1](#)).

6.4.6. Efficacy Assessments

6.4.6.1. Orthostatic Hypotension Questionnaire

The OHQ is a 2-component scale made up of a 6-item symptom assessment scale referred to as OHSA and a 4-item daily activity scale referred to as the OHDAS⁹. The items are scored on an 11-point scale from 0 to 10, with 0 indicating no symptoms/no interference and 10 indicating the worst possible symptoms/complete interference, and the option of selecting “cannot do for other reasons.” Assessments will be performed as specified in the Schedule of Study Procedures ([Table 1](#)). An example of the instrument is provided in [Appendix 2](#).

6.4.6.2. Patient Global Impression of Severity

Patient Global Impression of Severity is a 1-item patient rated questionnaire designed to assess the patient’s impression of symptom severity. The PGI-S item asks the respondent to best describe the current severity of symptoms of his/her neurogenic orthostatic hypotension on a 5-category scale, where a higher score is associated with greater symptom severity. Assessments will be performed as specified in the Schedule of Study Procedures ([Table 1](#)). An example of the instrument is provided in [Appendix 2](#).

6.4.6.3. Wearable Device

A wearable device, such as an activity monitor, that provides date- and time-stamped activity information will be used to collect raw motion data to measure the time spent in supine, sitting, and standing positions.

In countries where the wearable devices are available, 2 consecutive days of device use will be required on the days shown in [Table 1](#). The 2 consecutive days of device use should be within 5 days before the subsequent visit. Site coordinators will monitor subject compliance. If the site coordinator becomes aware that a subject has not used the device for the required time, they will contact the subject and remind them to use the device. Subjects will be identified by subject ID and no personally identifiable information is collected or stored.

In countries where the devices are available, assessments will be performed as specified in the Schedule of Study Procedures ([Table 1](#)).

6.4.6.4. Unified Parkinson's Disease Rating Scale

Unified Parkinson's disease Rating Scale, a clinical rating scale for PD, has nearly comprehensive coverage of motor symptoms and its clinimetric properties, including reliability and validity. The UPDRS is only for subjects with PD. It is made up of 6 parts, namely, 1: evaluation of mentation, behavior, and mood; 2: self-evaluation of the activities of daily living (ADLs), including speech, salivation, swallowing, handwriting, cutting food/handling utensils, dressing, hygiene, turning in bed/adjusting bedclothes, falling, freezing when walking, tremor, and sensory complaints; 3: clinician-scored monitored motor evaluation; 4: complications of therapy; 5: modified Hoehn and Yahr staging of severity of PD; and 6: modified Schwab and England ADL scale. Assessments will be performed as specified in the Schedule of Study Procedures ([Table 1](#)). The UPDRS scale should be completed in an ON state, and within 2-4 hours of taking the PD medications. All UPDRS Parts will be completed on Day 1 for De Novo Group subjects, while only Parts 2 and 3 of the questionnaire would be completed for 0169 Completers Group, and for subsequent visits. An example of the instrument is provided in [Appendix 2](#).

6.4.6.5. The Parkinson's Disease Questionnaire-8

The PDQ-8 is derived from the Parkinson's Disease Questionnaire-39 (PDQ-39) and is only for subjects with PD. The short-form 8-item PDQ-8 was developed to reflect scores on the PDQ-39 single index, but with a smaller number of items, placing less burden upon respondents. In the original formulation, 1 item was selected from each of the 8 dimensions of the PDQ-39. The item selected being the one that correlated most strongly with the dimension total to which it contributes. These 8 items constitute the PDQ-8 and are then summed to produce a single figure. Assessments will be performed as specified in the Schedule of Study Procedures ([Table 1](#)).

An example of the instrument is provided in [Appendix 2](#).

6.4.6.6. Unified Multiple System Atrophy Rating Scale

The UMSARS is only for subjects with MSA and comprises the following components: Part 1, historical review, 12 items; Part 2, motor examination, 14 items; Part 3, autonomic examination; and Part 4, global disability scale. Assessments will be performed as specified in the Schedule of Study Procedures ([Table 1](#)). An example of the instrument is provided in [Appendix 2](#).

6.4.6.7. Composite Autonomic Symptom Score-31

The COMPASS-31 is a refined, internally consistent, and markedly abbreviated quantitative measure of autonomic symptoms. It is based on the original Autonomic Symptom Profile (ASP) and Composite Autonomic Symptom Score (COMPASS), applies a more simplified scoring algorithm, and is suitable for widespread use in autonomic research and practice. It is only used for subjects with MSA. Assessments will be performed as specified in the Schedule of Study Procedures (Table 1). An example of the instrument is provided in Appendix 2.

6.4.6.8. Incidence of Falls – Subject Diary

Falls in subjects with symptomatic nOH are common and potentially catastrophic. They can lead to serious injuries including hip fractures or head trauma; furthermore, fear of falling can limit mobility and physical activity. Thus, incidence of subject-reported falls is being captured in a diary. Assessments will be performed as specified in the Schedule of Study Procedures (Table 1). An example of the instrument is provided in Appendix 3.

6.4.6.9. Orthostatic Standing Test

The orthostatic standing test (including SBPs) will be performed at the time points described in the Schedule of Study Procedures (Table 1).

At each time point, BP and HR measurements will be recorded with automated (or manual) sphygmomanometer while resting supine (with the torso and head elevated 30 degrees from horizontal), for a total of 10 minutes, with measurements taken at 5 and 10 minutes. Followed by, seated for a total of 10 minutes, with measurements taken at 5 and 10 minutes. Lastly, standing for up to a total of 10 minutes, with measurements taken at 1, 3, 5, and 10 minutes while standing. The standing time will be measured with a chronometer and the duration of standing will be recorded. The total duration of standing may occur in between the time points (i.e., 1, 3, 5, and 10 minutes) for the standing test. In either case, the total duration should be recorded. The BP and HR collected after 10 minutes supine and seated from the orthostatic standing test can be used for safety vital sign assessment. The assessments should be performed at approximately (± 2 hour) the same time of day on Day 1 (except Screening). Subjects should abstain from eating for at least 90 minutes prior to this assessment.

Assessments will be performed as specified in the Schedule of Study Procedures (Table 1).

6.4.7. Pharmacokinetic Assessments

A sparse PK sampling strategy is being employed in this study. At the time points described in the Schedule of Study Procedures (Table 1), blood samples for PK assay of TD-9855 will be collected, centrifuged, and split into aliquots. Detailed instructions and collection kits for sample collection, handling, and shipping will be provided in the laboratory manual.

All PK sampling times will be accurately recorded by collection date, hour, and minute. Study medication dosing time on the day before each PK collection and on the day of each PK collection will be accurately recorded by dosing date, hour, and minute by the study staff using time recorded in Dosing Diary by Subjects.

Assessments will be performed as specified in the Schedule of Study Procedures (Table 1).

6.4.8. Pharmacodynamic Assessments

At the time points described in the Schedule of Study Procedures ([Table 1](#)), blood samples for pharmacodynamic markers may be measured. Detailed instructions and collection kits for sample collection, handling, and shipping will be provided in the laboratory manual.

Blood samples for pharmacodynamic markers (DHPG and NE) will be collected at select study visits as defined in the Schedule of Study Procedures after the subject has been seated for 30 minutes. Note that all pharmacodynamic marker samples should be collected at approximately (± 1 hour) the same time of day. Time-matched sampling will enable time-matched analysis, which is critical for biomarkers of the NE pathway owing to diurnal variations. NE alone will also be collected at Screening Visit as part of the eligibility criteria evaluations.

Assessments will be performed as specified in the Schedule of Study Procedures ([Table 1](#)).

6.4.9. Exploratory Assessments

6.4.9.1. EQ-5D-5L Descriptive System

The EQ-5D-5L is a standardized measure of health status developed by the EuroQol Group in order to provide a simple, generic measure of health for clinical and economic appraisal. The EQ-5D-5L essentially consists of 2 pages: the EQ-5D descriptive system and the EQ visual analogue scale (EQ VAS).

The descriptive system comprises 5 dimensions: mobility, self-care, usual activities, pain/discomfort, and anxiety/depression. Each dimension has 5 levels: no problems, slight problems, moderate problems, severe problems, and extreme problems. The subject is asked to indicate his/her health state by ticking the box next to the most appropriate statement in each of the 5 dimensions.

The EQ VAS records the patient's self-rated health on a vertical visual analogue scale, where the endpoints are labelled, "The best health you can imagine" and "The worst health you can imagine." The EQ VAS can be used as a quantitative measure of health outcome that reflect the subject's own judgment. Assessments will be performed as specified in the Schedule of Study Procedures ([Table 1](#)). An example of the instrument is provided in [Appendix 2](#).

6.4.9.2. Non-Motor Symptom Scale

The NMSS is a 30-item scale for the assessment of non-motor symptoms. The NMSS contains 9 domains: cardiovascular including falls, sleep/fatigue, mood/cognition, perceptual problems/hallucinations, attention/memory, GI tract, urinary, sexual function, and miscellaneous. The NMSS can be used to assess the frequency and severity of non-motor symptoms in patients across all stages in conjunction with the validated non-motor questionnaire. Assessments will be performed as specified in the Schedule of Study Procedures ([Table 1](#)). An example of the instrument is provided in [Appendix 2](#).

6.4.9.3. Hospital Anxiety and Depression Scale

The HADS is a brief questionnaire comprised of 2 domains including anxiety (7-items) and depression (7-items). It has been validated for in-clinic and out-patient settings. Assessments will be performed as specified in the Schedule of Study Procedures ([Table 1](#)). An example of the instrument is provided in [Appendix 2](#).

6.4.9.4. Burden Scale for Family Caregivers – Short Version

The burden experienced by family caregivers is the most important caregiver-related variable in care at home of a chronically-ill person. The extent of subjective burden has significant impact on the emotional and physical health of the family caregiver, and even influences the mortality of spouse caregivers. It affects the way the family caregiver deals with the care-receiver and determines the time of institutionalization. The shorter version consists of the 10 statements of the BSFC-s and are rated on a 4-point scale ranging from 0 (strongly disagree) to 3 (strongly agree). Assessments will be performed as specified in the Schedule of Study Procedures (Table 1). An example of the instrument is provided in Appendix 2.

6.4.10. Safety Assessments

6.4.10.1. Columbia-Suicide Severity Rating Scale

The C-SSRS is a tool designed to systematically assess and track suicidal AEs (suicidal behavior and suicidal ideation). The strength of this suicide classification system is in its ability to comprehensively identify suicidal events while limiting the over-identification of suicidal behavior. The C-SSRS Baseline/Screening Version will be used at V1 and the C-SSRS Since Last Visit Version will be used for subsequent visits. Assessments will be performed as specified in the Schedule of Study Procedures (Table 1). An example of the instrument is provided in Appendix 2.

6.4.10.2. Adverse Events

Adverse events will be reviewed and recorded from signing of the informed consent through the end of follow-up. Adverse events may be observed by the study personnel or spontaneously reported by the subject.

Subjects entering from Study 0169 (0169 Completers Group): Adverse events that start after signing of Study 0170 informed consent, but before the first dose of study drug is taken on Day 2, are to be captured in Study 0169 database. Adverse events started in Study 0169 but which worsen in severity or seriousness during Study 0170 should be reported as a new adverse event.

All AEs must be recorded in the subject's CRF and, if applicable, reported as described in Section 7.

The Investigator must take all therapeutic measures necessary for resolution of AEs. Any medications necessary for the treatment of an AE must be recorded in the subject's CRF. Refer to Section 7.

Except where described above, the Investigator may prescribe medications to provide adequate supportive care. However, the Investigator should use judgment to avoid medications that may confound the interpretation of this study.

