6.4.10.3. Medication and Medical History

A complete medical history will be taken during the screening visit (for De Novo subjects only) and will include evaluation of past and present cardiovascular, respiratory, GI, renal, hepatic, neurological, endocrine, lymphatic, hematologic, immunologic, dermatologic, psychiatric, genitourinary, substance abuse, surgical history, or any other diseases or disorders. Medical conditions will be recorded for 2 years prior to screening visit, along with the date of diagnosis, and any other relevant medical history that has an impact to the subject.

Medical events or conditions that arise or worsen in severity or frequency after the signing of the informed consent will be recorded as an AE.

All medications used during the 60 days prior to screening will be recorded in the source records. The only exception is drugs that were used to treat previous orthostatic hypotension; these will be recorded since the time of primary diagnosis.

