6.4.10.5. Neurological Examination

Any abnormalities identified at the screening visit will be recorded as neurological medical history. Any abnormalities or symptoms reported during treatment that arise or worsen in severity or frequency will be reported as AEs.

The PI should perform a neurological exam in clinic or via telemedicine platform for remote visits (assisted as necessary by the home health nurse) as required to assess the subject's current condition and include the following exams per the PI's medical discretion.

The examination will assess the following:

- Cranial nerves (cranial nerves II-XII, excluding funduscopic examination)
- Motor system (tone, strength, and abnormal movements)
- Sensory system (light touch, pinprick, joint position, and vibration)
- Reflexes (deep tendon reflexes and plantar responses)
- Coordination (upper and lower extremities)
- Gait (base and tandem gait)
- Station (posture and stability)

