7.1.1. Adverse Event

An AE is any untoward medical occurrence in a clinical trial subject administered a pharmaceutical product that does not necessarily have to have a causal relationship with this treatment. An AE can therefore be any unfavorable and unintended sign (including an abnormal laboratory finding), symptom, or disease temporally associated with the use of a medicinal product, whether or not related to the medicinal product.

- AEs may be new events.
- AEs may be preexisting events that increase in frequency, severity, or change in nature or seriousness during or as a consequence of participation in clinical studies.
- AEs may be pre- or posttreatment complications that occur as a result of a protocol-mandated procedure (such as a biopsy).
- AEs may be clinically significant changes from baseline in physical examination, laboratory tests, or other diagnostic investigation (e.g., laboratory results, x-ray findings).
- AEs may result from an overdose of the study medication.

Whenever possible, the diagnosis (rather than a series of terms related to a diagnosis) should be recorded as the AE term.

An AE does not include the following:

- Medical or surgical procedures (such as surgery, endoscopy, tooth extraction, or transfusion); the condition that leads to the procedure is an AE
- Pre-existing diseases or conditions present or detected before signing an informed consent form (ICF) that do not worsen
- Situations where an untoward medical occurrence has not occurred (such as hospitalization for elective surgery or social and/or convenience admissions)
- Overdose of either study medication or concomitant medication without any signs or symptoms, unless the subject is hospitalized for observation

Any medical condition or clinically significant laboratory abnormality with an onset date prior to the time the subject signed the ICF is considered to be preexisting and should be documented in the medical history CRF.

Pregnancy is not an AE; however, if a female subject becomes pregnant during the conduct of the study, the sponsor will be notified according to the procedures for SAE reporting as outlined in Section 7.4.3. Follow-up information regarding the outcome of the pregnancy and any fetal or neonatal sequelae will be obtained and documented.

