8.6.2. Adverse Event Data

The AEs will be coded to the preferred terms (PTs) of the Medical Dictionary for Regulatory Activities (MedDRA[®]). Summaries will be presented by system organ class (SOC), PT, and severity (mild, moderate, severe), along with the number and percentage of subjects for whom events were reported.

For subjects continuing from OL phase to the double-blinded randomized withdrawal phase, an AE that begins on or after the date of the first dose of TD-9855 up to the date of last dose of TD-9855 in OL phase will be considered TEAE for OL phase. For subjects discontinuing the study during the OL phase, an AE that begins on or after the date of the first dose of TD-9855 and up to the date of last dose of TD-9855 plus 14 days follow-up period will be considered TEAE for OL phase.

In the double-blinded randomized withdrawal phase, a TEAE is defined as any AE that begins on or after the date of the first dose of study medication post randomization and up to the date of last dose of study medication plus 14 days follow-up period.

The number and percentage of subjects who experience TEAEs will be summarized. Summaries of TEAEs will include the following:

- All AEs, by SOC and PT and also by PT (by descending overall frequency)
- All AEs, by SOC, PT, and severity
- All study medication-related AEs, by SOC and PT
- All study medication-related AEs, by SOC, PT, and severity

- All AEs leading to premature discontinuation of study medication, by SOC and PT
- All AEs leading to temporary interruption of study medication, by SOC and PT
- All SAEs, by SOC and PT
- All study medication-related SAEs, by SOC and PT

All AEs reported will be listed by subject. A separate listing will be provided for all subjects who experience an SAE. Separate listings will also be provided for subjects who discontinued study treatment prematurely because of AEs and subjects who temporarily interrupted study treatment because of AEs. The AESIs, as described in Section 7.1.4, will be listed and summarized.

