9.1. Adverse Events

Adverse events are collected from signing of the informed consent form through the end of follow-up. Adverse events will be coded to the preferred terms of the Medical Dictionary for Regulatory Activities (MedDRA®, version 24.1).

A treatment-emergent adverse event (TEAE) will be defined as any AE that begins on or after the date of first dose of study drug up through 14 days after the date of last dose of study drug. AEs that begin more than 14 days after the date of last dose of study drug and AEs that begin during the period from obtaining informed consent to the start of administration of study drug will not be considered treatment-emergent and will be listed only.

The following AE summaries will be provided for each treatment period:

- TEAE overall summary
- TEAEs by preferred term
- TEAEs by system organ class and preferred term
- Moderate or severe TEAEs by system organ class and preferred term
- TEAEs by preferred term with frequency > 3% of safety analysis set subjects
- TEAEs by system organ class, preferred term, and severity
- Drug-related TEAEs by system organ class and preferred term
- Drug-related TEAEs by system organ class, preferred term, and severity
- Drug-related moderate or severe TEAEs by system organ class and preferred term
- Serious TEAEs by system organ class and preferred term
- Drug-related serious TEAEs by system organ class and preferred term
- TEAEs resulting in on-study deaths
- TEAEs leading to premature study drug discontinuation
- TEAEs leading to temporary interruption of study drug
- TEAEs of special interest by system organ class and preferred term (Section 9.1.1)

If no adverse events meeting a specific table definition were reported, the body of the table will contain only a statement that no events met the table definition.

The following AE listings will be provided:

- TEAEs
- AEs leading to premature study drug discontinuation
- AEs resulting in temporary interruption of study drug
- Serious adverse events
- Deaths
- Non-treatment-emergent adverse events
- Adverse events of special interest (Section 9.1.1)
- Adverse events for excluded site 27045 (Section 6.2.1)

9.1.1. [REDACTED]

[REDACTED]

- [REDACTED]
- [REDACTED]
- [REDACTED]
- [REDACTED]
- [REDACTED]
- [REDACTED]

[REDACTED]

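### Adverse events that start in open label and worsen on randomized treatment have no assured place in Study 0170's by-arm TEAE tables

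*Protocol*

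**What the plan says.** **Reporting.** Protocol 6.4.10.2, for subjects rolling over from the preceding study: "Adverse events started in Study 0169 but which worsen in severity or seriousness during Study 0170 should be reported as a new adverse event". This is the only sentence that orders a new report when an already recorded AE gets worse.

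Three more general statements touch on worsening:
- Protocol 6.4.10.3: "Medical events or conditions that arise or worsen in severity or frequency after the signing of the informed consent will be recorded as an AE".
- Protocol 6.4.10.5, on neurological findings: "Any abnormalities or symptoms reported during treatment that arise or worsen in severity or frequency will be reported as AEs".
- Protocol 7.1.1: "AEs may be preexisting events that increase in frequency, severity, or change in nature or seriousness during or as a consequence of participation in clinical" [trials]. The same section says that a condition "with an onset date prior to the time the subject signed the ICF is considered to be preexisting".

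**Analysis.** Protocol 8.6.2: "In the double-blinded randomized withdrawal phase, a TEAE is defined as any AE that begins on or after the date of the first dose", meaning the first dose after randomization, with the window closing 14 days after the last dose. For subjects who continue into the randomized phase, an AE that starts between the first and last open-label doses is an open-label TEAE.

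SAP 9.1: "A treatment-emergent adverse event (TEAE) will be defined as any AE that begins on or after the date of first dose of study drug". It then asks for a set of tables for each treatment period, among them TEAEs by severity, serious TEAEs, TEAEs of special interest and "TEAEs leading to premature study drug discontinuation". SAP 11.2 lists no change to the TEAE definition.

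**The concern.** Safety is a primary objective (Protocol 2.1), and the randomized period holds Study 0170's own comparison with placebo. Every randomized subject has first had 16 weeks of TD-9855, so some will have an AE ongoing at the first randomized dose. Those AEs are plausible candidates to change when the drug is continued or withdrawn: pressor events on TD-9855, orthostatic events on placebo.

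Suppose a hypertension AE begins mild in Week 14 and becomes severe, or the reason for stopping, in Week 18. If the site keeps one record, its onset stays in open label. By the onset rule it is not a randomized-period TEAE, so it is absent by arm from the severity, serious, special-interest and discontinuation tables. If the record carries the worst grade, a severity reached on randomized treatment is credited to the open-label column. The event would not reach the listing of non-treatment-emergent AEs either, because it is an open-label TEAE.

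At stake are the completeness of the by-arm AE tables and, if worsening differs between arms, the difference that they show.

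**Working it through.** **1. Is there a re-reporting rule at the first randomized dose?**

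| Protocol section | Does it cover an open-label AE that worsens after that dose? |
|---|---|
| 6.4.10.2 | No. Only AEs that began in Study 0169. |
| 6.4.10.3 | Unclear. Worsening is recorded as an AE, but nothing says an open AE gets a new record or start date. Severity and frequency are named, seriousness is not. |
| 6.4.10.5 | Unclear in the same way, and neurological findings only. |
| 7.1.1 | Not clearly. It speaks of preexisting events, and a preexisting condition is one with onset before consent. |
| 7.3 | No. Onset and resolution dates, severity, outcome and action taken are recorded; no date of worsening is listed. |
| 7.4.2 | No. It has an exception for Study 0169 completers and nothing on this boundary. |

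A site could open a new record under 6.4.10.3 or 6.4.10.5, or continue the old one. Handling may vary by site.

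**2. Does the TEAE definition catch the event anyway?** Under Protocol 8.6.2 it does so only if a new record with a later onset exists. SAP 9.1 runs from the first dose of study drug, is not period-specific, and does not say which period's tables an event enters. By contrast, Protocol 8.6.6 defines treatment-emergent ECG abnormalities to include those that worsened after treatment. The plan therefore uses a worsening criterion for ECGs and not for AEs.

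**3. Denominator.** Inputs from Protocol 8.2: 25% versus 50%, two-sided alpha 0.05, power 90%, total 154; 1:1 allocation from Protocol 5.1.

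n per arm = [1.960 × √(2 × 0.375 × 0.625) + 1.2816 × √(0.25 × 0.75 + 0.50 × 0.50)]² / 0.25²
= [1.3419 + 0.8477]² / 0.0625 = 4.794 / 0.0625 = 76.7, rounded up to 77.

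Two arms give 154, and power at 77 per arm is 90.1%. The plan's figure is reproduced.

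**4. Possible size.** The documents give no rate of ongoing or worsening AEs, so the rates below are assumptions. Let o be the share of subjects with an AE ongoing at the first randomized dose, w the share of those whose AE worsens, becomes serious or ends treatment within 6 weeks, and s the share of such events kept as one record.

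Uncounted subjects per arm = 77 × o × w × s

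- o = 0.20, w = 0.10, s = 1: 77 × 0.02 = 1.5
- o = 0.50, w = 0.20, s = 1: 77 × 0.10 = 7.7

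Taking s = 1 gives the maximum for each pair of rates. If every site opened a new record, s = 0 and nothing is lost.

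Effect on the difference between arms, with s = 1:

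| Assumed o × w, TD-9855 / placebo | Uncounted per 77 | Difference understated by |
|---|---|---|
| 2% / 2% | 1.5 / 1.5 | 0 points |
| 5% / 2% | 3.9 / 1.5 | 3 points |
| 10% / 5% | 7.7 / 3.9 | 5 points |

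With equal rates only the absolute incidence is understated. If worsening were commoner on placebo, the shift would reverse.

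**The case against.** A reader might infer that such events vanish from the placebo-controlled comparison altogether. The documents do not support that, and this part of the opposing case stands:
- Non-completion of the randomized period because of an AE is counted by arm with no condition on onset date (SAP 7.2).
- Anyone who withdraws before V9 is a primary-endpoint failure (Protocol 3.4.1).
- Serious AEs and AEs that led to discontinuation are listed, and those listings are not confined to TEAEs (SAP 9.1).
- Blood pressure, its change and its extreme values are summarized by period and arm (SAP 6.1 and 9.5), so the hypertension example would leave a trace there.
- The data monitoring committee reviews unblinded safety data (Protocol 6.8.4).
- Study 0169 also had a placebo arm, as the rollover columns in SAP 6.1 show.

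These sources do not replace the tables. Disposition gives a reason without term, severity or relatedness, and its AE count could exceed the discontinuation-TEAE count for the same arm with nothing in the plan to explain the gap.

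A second argument is that the sentence in 6.4.10.2 only manages a hand-off between two studies, so its absence within one study shows no oversight. That is fair as to motive, but the onset-only definition has the same effect whatever the motive.

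Third, a rule could exist where it cannot be seen: the CRF completion guidance is not among the documents, and the text of SAP 9.1.1 and 11.1.1 to 11.1.3 is redacted. That cannot be excluded, although the contents page places 11.1.1 to 11.1.3 under missing-data handling.

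Fourth, subjects with intolerable AEs or sustained high blood pressure leave during open label, so those randomized are selected for tolerability. This argues for the lower end of the assumed range.

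**Conclusion.** The point holds as a gap in the by-arm TEAE tables. As written, an open-label AE that is kept as one record and becomes more severe, serious or treatment-ending after the first randomized dose is not a randomized-period TEAE. Whether it is kept as one record is left to the site.

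The size cannot be computed from the documents. The 2% to 10% of subjects, about 1.5 to 7.7 of 77 per arm, rests on assumed rates and on every such event staying unsplit. It is an illustration of scale. The 77 is the planned number; the SAP provides for termination by the sponsor, so the actual arms may be smaller.

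It would go too far to say that a real difference in worsening would be reported as zero in both arms. That would need every site to keep a single record despite Protocol 6.4.10.3 and 6.4.10.5, and would ignore the other by-arm outputs. The gap is still worth closing, because safety is a primary objective and the remedy is conventional and cheap.

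**What to change.** 1. In Protocol 8.6.2 and SAP 9.1, define a randomized-period TEAE as an AE that begins, or worsens in severity or seriousness, on or after the first randomized dose. Add an explicit rule that assigns each event to a period.
2. In Protocol 6.4.10.2 and 7.4.2, extend the existing new-AE sentence to AEs ongoing at the first randomized dose that later worsen in severity or seriousness.
3. For data already collected, add a by-arm table of AEs ongoing at the first randomized dose, with worst severity, seriousness, outcome and action taken. In the randomized-period discontinuation table, include any AE that led to stopping randomized drug, regardless of onset date.

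The cost is one reporting sentence, one derivation rule and one extra table. There is a limit: the SAP describes randomization in the past tense (4.4), so item 2 may come too late for most of the data, and worsening may not be datable for unsplit records. Item 3 needs no worsening date and draws on fields that Protocol 7.3 already collects, so it is the part that remains workable in any case.
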